7.2.3 PROMIS Parent Proxy Pain Behavior Short Form (8a)

The PROMIS is a system of highly reliable, precise measures of patient-reported health status for physical, mental, and social well-being. These tools can be used as primary or secondary endpoints in clinical studies of the effectiveness of treatment and can be used across a wide variety of chronic diseases and conditions and in the general population.

Pain behaviors, such as verbal complaints of pain and suffering, non-language sounds, facial expressions, body posturing and gesturing, and limitations in activities, demonstrate to others that an individual is experiencing pain. The PROMIS Parent Proxy Pain Behavior item bank contains 39 items specific to pain behaviors. From this item bank, a short form (8a) was developed specific to caregiver reports and consists of 8 pain behaviors assessed across a 6-point scale from "had no pain" to "almost always." ⁵⁵

This assessment will be administered to caregivers of children <3 years of age and will be performed at baseline, then daily through Week 6, followed by weekly to Week 24.

7.2.4 Pain Medication Log

A pain medication log will be kept for all participants. While participants are hospitalized, the log will be completed by study staff. While participants are not hospitalized, they (or their parents or other caregivers) will enter their medication information into the log. Pain medications and antispasmodics will be collected in the log.

These assessments will be administered at baseline and then daily through Week 6 followed by weekly to Week 24.

7.2.5 Urinary Frequency and Nocturia Items from the Interstitial Cystitis Symptoms Index

The ICSI and Interstitial Cystitis Problem Index (ICPI) are 2 brief, self-reported assessments designed to be utilized together to assess lower urinary tract symptoms and problems in participants with interstitial cystitis.⁵⁶ These measures are widely used and well established with acceptable measurement properties. In this study, only items 2 and 3 from the ICSI will be administered. These items assess urinary frequency (During the past 7 days, have you had to urinate less than 2 hours after you finished urinating?) and nocturia (During the past 7 days, how often did you most typically get up at night to urinate?). The ICPI will not be administered.

This item will be administered to participants ≥12 years of age at baseline, weekly through Week 6, and then at Weeks 8, 12, 16, and 24. It has been adapted to capture symptoms over the preceding 7 days, rather than over the preceding month. In the event that the participant has an indwelling urinary catheter (including a 3-way catheter for continuous bladder irrigation), for the duration of catheterization this item will not be administered.

7.2.6 Age-Appropriate Global Impression Scales

The PGIC and CGIC scales consist of 1 question each to be completed by either the participant or the caregiver, respectively, to assess the overall change in HC symptoms. The PGIS and CGIS consist of 1 question each to be completed by either the participant or the caregiver, respectively, to assess overall severity of symptoms.

Age-appropriate versions of the PGIC will be administered to those 8 to 11 years of age, and ≥12 years of age. Age-appropriate versions of the PGIS will be administered to those 3 to 7 years of age, 8 to 11 years of age, and ≥12 years of age. The CGIC will be administered to caregivers of children <8 years of age. The CGIS will be administered to children <3 years of age.

The PGIS and CGIS will be administered at baseline, daily through Week 6, and then weekly to Week 24. The PGIC and CGIC will be administered starting on the day of the first infusion, daily through Week 6, and then weekly to Week 24.

7.2.7 EQ-5D-5L, EQ-5D-Y, and EQ-5D-Y Proxy Version 1

The EQ-5D is a group of instruments that was developed to assess patient-reported health-related quality of life.⁵⁷ The EQ-5D-5L includes the EQ-5D descriptive system and the EQ visual analog scale (EQ VAS). The EQ-5D descriptive system comprises 5 dimensions: mobility, self-care, usual activities, pain/discomfort, and anxiety/depression. In the EQ-5D-5L, each dimension has 5 levels: no problems, slight problems, moderate problems, severe problems, and extreme problems. The participant is asked to indicate his or her health state by checking the box next to the most

appropriate statement in each of the 5 dimensions. The versions used in children have 3 responses to each question instead of 5.

In this study, the EQ-5D-5L will be used for individuals ≥12 years of age, the EQ-5D-Y for children 8 to 11 years of age, and the EQ-5D-Y Proxy Version 1 for children ≤7 years of age. Data for children <4 years of age will also be collected using the EQ-5D-Y Proxy Version 1, but these results will be analyzed separately from the results for children 4 to 7 years of age.

The EQ-5D-5L, the EQ-5D-Y, and the EQ-5D-Y Proxy Version 1 include the EQ VAS. The EQ VAS records the participant's self-rated health on a vertical visual analog scale, where the endpoints are labeled "The best health you can imagine" and "The worst health you can imagine."

These assessments will be administered at baseline, weekly through Week 6, and then at Weeks 8, 12, 16, and 24.

7.2.8 Planned Exit Interview

Approximately 35 participants at selected sites in countries where English is the primary language may provide additional informed consent to participate in a single participant interview. The interview may be conducted via telephone and will take place approximately 10 days following the Week 24/Early Termination visit and following participant discharge from the hospital (if applicable).

Participant interviews will be conducted over the telephone by highly trained interviewer(s) from Research Triangle Institute Health Solutions, Research Triangle Park, NC 27709, USA utilizing a semi-structured interview guide developed in collaboration with AlloVir.

The participant interview is designed to examine the experience of HC from the perspective of participants and caregivers of pediatric participants, including perceptions of symptom severity and variability, symptom burden, and disease-related impacts, as well as experiences during this clinical study. Participants will also be asked to provide their thoughts about the magnitude of meaningful changes on selected COAs utilized in the study. The participant interview will take approximately 60 minutes. Any adverse event(s) mentioned by a participant or caregiver during the interview will be captured by the interviewer and communicated to the site within the same business day to enable site staff to follow up and report as per protocol requirements.

A detailed description of the participant interview and all related procedures is provided in the Patient Interview Procedures Guide that will be provided separately to the sites.

7.3 Resolution of Viral Infections

In participants with concomitant viral infections at the time of treatment, peripheral blood and, where relevant, urine, will be monitored for BKV, AdV, CMV, HHV-6, JCV, and/or EBV viral load (Appendix A). Resolution of viral infection will be defined as a return to normal range as defined by the assay used and complete resolution of clinical signs and symptoms as determined by the Investigator.

Samples for viral sequence/genotype will be collected on all participants as indicated in Appendix A.

8 SAFETY ASSESSMENTS

The safety endpoints for this study include the following:

- Incidence and severity of acute GVHD (secondary endpoint) (for the acute GVHD grading scale, see Appendix E)
- Incidence and severity of chronic GVHD (exploratory endpoint) (for the chronic GVHD grading scale, see Appendix E)
- Incidence and severity of CRS (secondary endpoint) (for the CRS grading scale, see Appendix F)

Safety will be evaluated throughout the duration of the study as indicated in Appendix A.

8.1 Adverse Events

An adverse event is defined as any untoward medical occurrence in a clinical investigation subject administered a pharmaceutical product, which does not necessarily have a causal relationship with this treatment. An adverse event can therefore be any unfavorable and/or unintended sign (including an abnormal laboratory finding), symptom, or disease temporally associated with the use of an investigational medicinal product, whether or not related to the investigational medicinal product. All adverse events, including observed or volunteered problems, complaints, or symptoms, are to be recorded on the appropriate eCRF.

Adverse events, which include clinical laboratory test variables, will be monitored and documented from informed consent until study participation is complete or until resolution, whichever is sooner. For participants who screen fail, only SAEs will be collected (see Section 4.5 for details). Participants should be instructed to report any adverse event that they experience to the Investigator, whether or not they think the event is due to study treatment. Beginning at informed consent, Investigators should make an assessment for adverse events at each visit and record each event on the appropriate adverse event eCRF.

Wherever possible, a specific disease or syndrome rather than individual associated signs and symptoms should be identified by the Investigator and recorded on the eCRF. However, if an observed or reported sign or symptom is not considered a component of a specific disease or syndrome by the Investigator, it should be recorded as a separate adverse event on the eCRF. Additionally, the condition that led to a medical or surgical procedure (eg, surgery, endoscopy, tooth extraction, or transfusion) should be recorded as an adverse event, not the procedure itself.

Any medical condition already present at informed consent should be recorded as medical history and not be reported as an adverse event unless the medical condition or signs or symptoms present at baseline increase in severity, frequency, or seriousness at any time during the study. In this case, it should be reported as an adverse event.

Clinically significant abnormal laboratory or other examination (eg, electrocardiogram [ECG]) findings that are detected during the study or are present at randomization and significantly worsen during the study should be reported as adverse events, as described below. The Investigator will exercise his or her medical and scientific judgment in deciding whether an abnormal laboratory finding or other abnormal assessment is clinically significant. Clinically significant abnormal laboratory values occurring during the clinical study will be followed until repeat tests return to normal, stabilize, or are no longer clinically significant. Abnormal test results that are determined

to be an error should not be reported as an adverse event. Laboratory abnormalities or other abnormal clinical findings (eg, ECG abnormalities) should be reported as an adverse event if any of the following are applicable:

- If an intervention is required as a result of the abnormality
- If action taken with the study drug is required as a result of the abnormality
- Based on the clinical judgment of the Investigator

The relevant AE, abnormality, or SAE should be followed to the point of resolution or until the event is considered stable, clinical insignificant, or asymptomatic.

If the home health provider identifies or records any new or updated signs or symptoms, the Investigator should be notified immediately.

8.1.1 Adverse (Drug) Reaction

All noxious and unintended responses to a medicinal product related to any dose should be considered an adverse drug reaction. "Responses" to a medicinal product means that a causal relationship between a medicinal product and an adverse event is at least a reasonable possibility, ie, the relationship cannot be ruled out. Section 8.1.3 provides further guidance on assessing the causal relationship between an adverse event and the medicinal product.

8.1.2 Unexpected Adverse Drug Reaction

An unexpected adverse drug reaction is defined as an adverse reaction, the nature or severity of which is not consistent with the applicable product information. For PSL, the reference safety information is included in the safety review in Section 7 of the IB currently in force. The reference safety information will be reviewed yearly, and the periodicity of the review will be harmonized with the reporting period of the Development Safety Update Report.

8.1.3 Assessment of Adverse Events by the Investigator

The Investigator will assess the severity (intensity) of each adverse event and will also categorize each adverse event as to its potential relationship to study drug using the categories of yes or no.

Assessment of Severity

The severity of all adverse events will be graded according to CTCAE version 5.0. For those adverse event terms not listed in the CTCAE, the following grading system should be used:

- CTCAE Grade 1: Mild; asymptomatic or mild symptoms; clinical or diagnostic observations only; intervention not indicated
- CTCAE Grade 2: Moderate; minimal local or noninvasive intervention indicated; limiting age-appropriate instrumental activities of daily living
- CTCAE Grade 3: Severe or medically significant but not immediately life-threatening; hospitalization or prolongation of hospitalization indicated; disabling; limiting self-care activities of daily living
- CTCAE Grade 4: Life-threatening consequences; urgent intervention indicated
- CTCAE Grade 5: Death related to the adverse event

Causality Assessment

The relationship of an adverse event to the administration of the study drug is to be assessed according to the following definitions:

No (not related, unlikely to be related) – The time course between the administration of study drug and the occurrence or worsening of the adverse event rules out a causal relationship and another cause (concomitant drugs, therapies, complications, etc.) is suspected.

Yes (possibly, probably, or certain to be related) – The time course between the administration of study drug and the occurrence or worsening of the adverse event is consistent with a causal relationship and no other cause (concomitant drugs, therapies, complications, etc.) can be identified.

The definition implies a reasonable possibility of a causal relationship between the event and the study drug. This means that there are facts (evidence) or arguments to suggest a causal relationship.

The following factors should also be considered:

- The temporal sequence from study drug administration-
 - The event should occur after the study drug is given. The length of time from study drug exposure to event should be evaluated in the clinical context of the event.
- Underlying, concomitant, intercurrent diseases-
 - Each report should be evaluated in the context of the natural history and course of the disease being treated and any other disease the participant may have.
- Concomitant drug-
 - The other drugs the participant is taking or the treatment the participant receives should be examined to determine whether any of them might be recognized to cause the event in question.
- Known response pattern for this class of study drug-
 - Clinical and/or preclinical data may indicate whether a particular response is likely to be a class effect.
- Exposure to physical and/or mental stresses-
 - The exposure to stress might induce adverse changes in the recipient and provide a logical and better explanation for the event.
- The pharmacology and pharmacokinetics of the study drug-
 - The known pharmacologic properties (absorption, distribution, metabolism, and excretion) of the study drug should be considered.

Serious adverse events will be reviewed by the Sponsor Medical Monitor, in consultation and with the global safety physician and further queries issued, if necessary. If there is a disagreement between the Investigator and the Sponsor's Medical Monitor regarding the designation of an event as serious (in line with the appropriate protocol definition), and/or regarding the plausibility of causality of an adverse event, the case will be referred to the DSMB for adjudication. Relevant information will be provided to the DSMB in parallel with the reports prepared for the next planned

data review meeting for evaluation at that meeting. Until the DSMB issues its response, the Investigator's designation will be respected.

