3.2 Data and Safety Monitoring Board

An independent Data and Safety Monitoring Board (DSMB) will be convened for this study to routinely monitor participant safety and evaluate prespecified interim analyses to determine whether to stop the study early for futility or success. The DSMB will receive summary reports of all serious adverse events (SAEs) and adverse events of special interest (AESI; see Section 8.1.4) at least monthly. In addition, the DSMB will receive expedited reporting of all individual,

unexpected, related SAEs occurring within 14 days of an infusion of study drug, and infusion-related AESI of at least Grade 2 severity occurring within 24 hours of an infusion. A DSMB charter, detailing all aspects of the DSMB's composition, scope of review, and procedures will be described in a separate document. In addition, the DSMB will review safety data at the following times: 1) after 9 to 15 participants have been randomized and then again at routine intervals; 2) after five children ≥1 and <6 years of age have been randomized; and 3) at additional ad hoc meeting(s) if determined necessary by the Sponsor or DSMB Chair. The DSMB will review the pre-specified interim analysis to determine whether to stop the study early for futility or success (described in Section 9.2.3). An unblinded statistician will be assigned to the DSMB. This statistician will not be involved in any aspects of study conduct outside of the DSMB, and their role will be defined in the DSMB charter.

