4.3.2 Discontinuation of Study Treatment

The following do not fulfill any of the criteria for withdrawal from the study but do make the participant ineligible to receive any additional infusions of study treatment:

• Development of irreversible, life-threatening, Grade 3 to 4 acute GVHD or a Grade 3 to 4 non-hematologic adverse event between the first and second doses of PSL or placebo that is

considered related to study treatment administration. If this occurs, the participant's toxicities will be followed until resolution or until the participant's participation in the study ends.

- Receipt of any other hematopoietic stem cell product.
- Receipt of therapy for relapse of the participant's primary malignancy.
- Occurrence of Grade 3 or 4 CRS that persists beyond 72 hours. If this occurs, the participant's toxicities will be followed until resolution or until the participant's participation in the study ends.
- Pregnancy.

If any of the above criteria are met, every effort should be made to keep the participant in the study and continue follow-up.

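### The Yes and No causality definitions in Protocol 8.1.3 leave two of four situations unclassified and conflict with 8.1.1, so related events can be under-counted and classified differently between sites

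*Protocol*

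**What the plan says.** Protocol 8.1.3 has the investigator judge the relationship of each adverse event to study drug "using the categories of yes or no". There is no third category.

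- **No** applies when the time course "rules out a causal relationship and another cause (concomitant drugs, therapies, complications, etc.) is suspected".
- **Yes** applies when the time course "is consistent with a causal relationship and no other cause (concomitant drugs, therapies, complications, etc.) can be identified". Its label is wider than that: "Yes (possibly, probably, or certain to be related").
- The paragraph after the two definitions says that they imply a reasonable possibility of a causal link, and adds: "This means that there are facts (evidence) or arguments to suggest a causal relationship". A list of factors to weigh follows, including underlying disease and concomitant drugs.

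Protocol 8.1.1 defines an adverse reaction as one where the causal relationship "is at least a reasonable possibility, ie, the relationship cannot be ruled out", and refers to 8.1.3 for guidance on making that judgement.

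The SAP gives no causality definition of its own. Section 3.5.1 tabulates treatment-related TEAEs, AESIs and serious events.

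**The concern.** Each definition joins two conditions with *and*, and the second pair is not the complement of the first. Events that meet one condition of each definition have no home. The most important such event has timing compatible with the drug and some other candidate cause. All participants are allogeneic transplant recipients, and Protocol 1.5.1 names GVHD as a main risk of the product. For GVHD the transplant itself is an obvious alternative explanation.

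The yes/no call is used in several places:

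- Protocol 3.2: expedited DSMB reports cover "unexpected, related SAEs occurring within 14 days of an infusion of study drug".
- Protocol 8.5: SUSARs are suspected reactions, with 7-day and 15-day reporting limits.
- Protocol 8.3.1: once participation is complete, the duty to report covers only serious events that the investigator considers related.
- Protocol 4.3.2: one criterion for ineligibility for further infusions covers Grade 3 to 4 non-hematologic events "considered related to study treatment administration".
- Protocol 9.2.2 and SAP 3.5.1: tables by relationship to treatment.

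A rule that leaves these events without a class makes all five depend on how each investigator resolves the gap.

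**Working it through.** No sample size, error rate or event count enters this point, so the check is an enumeration. The inputs are the two definitions in Protocol 8.1.3 and the standard in 8.1.1. Cross the two conditions that 8.1.3 uses: timing (compatible or ruled out) and another cause (present or absent).

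| Timing | Other cause | 8.1.3 read literally | 8.1.1 standard |
|---|---|---|---|
| Compatible | Absent | Yes | Related |
| Compatible | Present | No class | Related, unless the link can be ruled out on other grounds |
| Ruled out | Present | No | Not related |
| Ruled out | Absent | No class | Not related |

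Step by step:

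1. Row 2 fails Yes because another cause can be identified. It fails No because the timing does not rule the drug out.
2. Row 4 fails Yes because the timing is not compatible. It fails No because no other cause is suspected.
3. Two of the four combinations therefore have no class on a form that accepts only two answers.
4. Row 2 is where 8.1.3 and 8.1.1 part. A second candidate cause does not by itself rule out the first, so 8.1.1 would normally count these events as related. The literal Yes in 8.1.3 cannot. Row 4 is a gap in the wording only, since 8.1.1 settles it as not related.
5. The labels do not repair this. The Yes label includes possibly related events, while its definition demands that no alternative be identifiable. The No label takes in events unlikely to be related, while its definition demands timing that excludes the drug. By label alone, a row 2 event could be entered as either.

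If investigators apply the Yes sentence literally and enter row 2 events as No, fewer related events are recorded than 8.1.1 would give. If some follow the Yes label or 8.1.1 and others do not, similar events are coded differently between sites. The documents give no event rates by timing and alternative cause, so the difference has no computable size.

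**The case against.** The strongest reply is that the surrounding text already steers investigators correctly. The Yes label includes possibly related events, the next paragraph speaks of a reasonable possibility, and 8.1.1 presents 8.1.3 as guidance on its own standard. The instruction to weigh underlying disease and concomitant drugs would have little purpose if any alternative cause automatically barred a Yes. This stands as mitigation: some investigators will answer Yes. It does not remove the conflict, because the operative definition says otherwise.

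A reader might infer that related events *will* be under-counted. The documents do not support that certainty. The literal No excludes row 2 events as firmly as the literal Yes does, so the text alone fixes no direction.

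A reader might also infer that GVHD or cytopenia could slip past the second-infusion rules through this gap. That goes too far. The adverse-event criterion in 4.3.2 is limited to non-hematologic events, so cytopenia does not enter it. Under Protocol 6.5.1, worsening GVHD at the proposed time of the second dose bars that infusion whatever its cause. The persistent CRS criterion in 4.3.2 carries no relatedness condition either.

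The safeguards are real:

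- Serious events during participation are reported within 24 hours regardless of causality (Protocol 8.3.1), as are AESIs (8.1.4).
- The DSMB receives summaries at least monthly with no relatedness filter: all SAEs and AESIs in Protocol 3.2, unexpected SAEs and AESIs in SAP 3.6.
- The Medical Monitor reviews serious events, and causality disagreements go to the DSMB (8.1.3).
- The SAP tabulates TEAEs, serious events and AESIs by arm irrespective of cause.

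The referral route is only partial. It feeds the next planned review meeting, and the investigator's call stands until the DSMB responds.

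**Conclusion.** The two definitions in Protocol 8.1.3 are not exhaustive, and the Yes definition contradicts its own label, the paragraph that follows it, and 8.1.1. Related events *can* be under-counted and can be classified inconsistently between sites. Under-counting rests on the assumption that at least some investigators apply the Yes sentence as written and default to No; inconsistency requires only that they resolve the gap differently.

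The effect is confined to outputs that use the relatedness label, as listed above. It would be wrong to read this as bias in the main safety comparison: all-causality tables by randomized, blinded arm do not use the label and are unaffected. The size cannot be computed from the documents. The point is worth correcting because the wording sets a conflicting rule, rather than merely omitting detail, and correction is cheap.

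**What to change.** Reconcile 8.1.3 with 8.1.1 by replacing the two definitions:

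- **Yes:** there is a reasonable possibility that study drug caused or contributed to the event, even if another cause is also possible.
- **No:** there is no reasonable possibility that study drug caused or contributed to the event.

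Every row of the table then falls in exactly one class. Bring the bracketed labels into line with the new sentences, and carry the same text into the eCRF completion guidance. The list of factors to weigh can stay as it is.

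The cost is two sentences in the protocol plus the eCRF guidance. The downside is that more events will be labelled related, which may raise the number of expedited reports. The same blinded threshold would apply in both arms, although the resulting counts need not be equal. No endpoint, sample size or efficacy analysis changes. The 4.3.2 criterion is left as written, but because it uses the relatedness call, the sponsor should confirm that the reconciled definition is the one intended there.

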8.2 Serious Adverse Events

An adverse event or adverse reaction is considered serious if, in the view of either the Investigator or Sponsor, it results in any of the following outcomes:

- Death.
- A life-threatening adverse event.

Note: An adverse event or adverse reaction is considered "life-threatening" if, in view of either the Investigator or Sponsor, its occurrence places the participant at immediate risk of death. It does not include an event that, had it occurred in a more severe form, might have caused death.

• Requires hospitalization or prolongation of existing hospitalizations.

Note: Any hospital admission with at least 1 overnight stay will be considered an inpatient hospitalization. An emergency room or urgent care visit without hospital admission will not be recorded as an SAE under this criterion, nor will hospitalization for a procedure scheduled or planned before signing of informed consent, or elective treatment of a pre-existing condition that did not worsen from baseline. However, unexpected complications and/or prolongation of hospitalization that occur during elective surgery should be recorded as adverse events and assessed for seriousness. Admission to the hospital for social or situational reasons (ie, no place to stay, live too far away to come for hospital visits, respite care) will not be considered inpatient hospitalizations.

- A persistent or significant disability/incapacity or substantial disruption of the ability to conduct normal life functions.
- A congenital anomaly/birth defect.

• An important medical event.

Note: Important medical events that do not meet any of the above criteria may be considered an SAE when, based upon appropriate medical judgment, they may jeopardize the participant and may require medical or surgical intervention to prevent one of the outcomes listed above. Examples of such medical events include allergic bronchospasm requiring intensive treatment in an emergency room or at home, blood dyscrasias or convulsions that do not result in inpatient hospitalizations, or the development of drug dependency.

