8.5 Expedited Reporting

The Sponsor/designee will report all relevant information about SUSARs that are fatal or life-threatening as soon as possible to the FDA, applicable competent authorities in all the Member States concerned, and the Central Ethics Committee, and in any case no later than 7 days after knowledge by the Sponsor/designee of such a case. Relevant follow-up information will subsequently be communicated within an additional 8 days.

All other SUSARs will be reported to the FDA, applicable competent authorities in all the Member States concerned, and the Central Ethics Committee as soon as possible but within a maximum of 15 days of first knowledge by the Sponsor/designee.

The Sponsor/designee will also report any additional expedited safety reports required in accordance with the timelines outlined in country-specific legislation.

The Sponsor/designee will also inform all Investigators as required per local regulation.

The requirements above refer to the requirements relating to the investigational medicinal product.

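### Protocol 8.1.3 holds a disputed event at the Investigator's rating until the DSMB responds; this contradicts 8.2 on seriousness and leaves 8.5 unclear on whose rating triggers an expedited report

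*Protocol*

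**What the plan says.** Protocol 8.1.3 covers disagreement between the Investigator and the sponsor's Medical Monitor on seriousness and/or causality. On the causality limb it reads: "regarding the plausibility of causality of an adverse event, the case will be referred to the DSMB for adjudication". On timing: "Relevant information will be provided to the DSMB in parallel with the reports prepared for the next planned" data review meeting, where the case is evaluated. It closes with: "Until the DSMB issues its response, the Investigator's designation will be respected".

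Protocol 8.2 sets the seriousness rule: an event is "considered serious if, in the view of either the Investigator or Sponsor, it results in any of the following outcomes". The note on life-threatening events repeats the either-party test: "if, in view of either the Investigator or Sponsor, its occurrence places the participant at" immediate risk of death.

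Protocol 8.5 sets the sponsor's reporting limits for SUSARs. Fatal or life-threatening cases go out as soon as possible and "in any case no later than 7 days after knowledge by the Sponsor/designee of such a case"; all others go out within 15 days of first knowledge.

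Protocol 3.2 says the DSMB reviews safety data "after 9 to 15 participants have been randomized and then again at routine intervals", with ad hoc meetings if the Sponsor or the DSMB Chair finds them necessary. SAP 3.6 leaves meeting frequency to the DSMB charter, which is not among the documents.

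**The concern.** Section 8.1.3 works in both directions. It stops the sponsor from lowering a site's rating during a dispute, which is protective. It equally stops the sponsor from raising one, and there the difficulty lies. An event that only the sponsor considers serious is serious at once under 8.2 but not serious under 8.1.3 until the DSMB has answered. Safety staff cannot apply both rules.

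Causality disputes are foreseeable. The definitions in 8.1.3 reserve a related rating for events with compatible timing and no other identifiable cause, and an unrelated rating for events whose timing excludes a link. An event with compatible timing and another plausible cause fits neither. Section 8.1.1 asks only whether a relationship can be excluded and does not say by whom.

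At stake is whether a suspected unexpected serious reaction reaches regulators, other investigators and the DSMB on time while infusions continue. Sample size, power and type I error are not affected.

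**Working it through.** The plan states no figure on this point, so there is none to reproduce. The check is a comparison of the texts, plus one timing calculation on an assumed input.

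**1. Seriousness.** Take an event that the sponsor rates serious and the Investigator does not.
- Under 8.2 it is serious, because one party's view suffices.
- Under 8.1.3 it is not serious until the DSMB responds.

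The two results are incompatible. The same holds for life-threatening status, which also decides which limit in 8.5 applies.

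**2. Causality.** Section 8.2 has no either-party rule for relatedness, and 8.1.1 names no decision-maker. Section 8.1.3 is therefore the only text on a pending causality dispute, and it points to the Investigator's rating.

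**3. Reporting limits.** Section 8.5 counts from the sponsor's knowledge. It does not pause for a disputed case and does not say whose rating makes a case a SUSAR. Whether the 8.1.3 hold extends to expedited reporting is left open.

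**4. Length of the hold.** Let T be the number of days between planned meetings. The documents do not give T, so it is an assumption. If a dispute arises at a uniformly random time between meetings, the share that waits longer than c days is max(0, 1 − c/T). For T = 30: 1 − 7/30 = 0.767 and 1 − 15/30 = 0.500.

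| Assumed T (days) | Mean wait, T/2 (days) | Wait > 7 days | Wait > 15 days |
|---|---|---|---|
| 7 | 3.5 | 0% | 0% |
| 14 | 7 | 50% | 0% |
| 30 | 15 | 77% | 50% |
| 60 | 30 | 88% | 75% |
| 91 | 45.5 | 92% | 84% |
| 182 | 91 | 96% | 92% |

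Every wait falls within 7 days only if planned meetings are at least weekly, and within 15 days only if they are at least every 15 days. This counts the wait for the meeting, not the time the DSMB then takes to respond. The at-least-monthly schedule in Protocol 3.2 and SAP 3.6 is for summary reports, not meetings.

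**5. Does the DSMB hear by another route?** Expedited notice under Protocol 3.2 has two limbs.
- The first covers SAEs that are both unexpected and related and arise in the 14 days after an infusion. It depends on the ratings in dispute.
- The second covers infusion-related AESI of Grade 2 or higher within 24 hours of an infusion. It needs no seriousness rating but is narrow.

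The at-least-monthly summaries include AESI whatever their rated seriousness or relatedness. An event that is not an AESI and that the site calls non-serious could appear in none of these.

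**The case against.** The strongest reply is that 8.1.3 and 8.5 can be read together. Section 8.1.3 never says that expedited reporting waits for the DSMB. The site's rating could stand as recorded while the sponsor, acting on its own knowledge, reports under 8.5. The sponsor can also call an ad hoc meeting, and the unseen charter may set short intervals. This stands as far as it goes: delay in reporting is possible, not shown. It does not remove the conflict with 8.2. It also relies on an interpretation the text does not state, and 8.1.3 does not use the ad hoc route.

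A reader might infer more in three respects, and the documents do not support it.
- That 8.1.3 contradicts 8.2 on relatedness as well. The either-party wording in 8.2 covers seriousness and life-threatening status only.
- That most disputed cases would breach the 7-day limit. That limit covers only fatal or life-threatening SUSARs, and both limits require the reaction to be unexpected against the Investigator's Brochure. The table gives waiting times for a meeting, not missed reports.
- That a disputed GVHD flare could go unseen. New or worsening GVHD is an AESI, submitted within 24 hours (8.1.4) and summarized for the DSMB at least monthly. Worsening at the time of the second dose bars that infusion whatever its cause (3.1 and 6.5.1).

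**Conclusion.** The concern holds in two parts. For seriousness and life-threatening status, 8.1.3 and 8.2 contradict each other on their face whenever the sponsor's rating is the higher one; this needs no assumption. For causality there is no direct contradiction, but 8.5 does not say whose rating governs a disputed case, so the hold, if applied to reporting, could outlast the 7-day and 15-day limits. How often depends on the assumed meeting interval and on disputes arising evenly over time. The number of disputes cannot be estimated from the documents. This is a safety-reporting inconsistency that should be fixed, with no bearing on the efficacy analyses.

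**What to change.** Reconcile Protocol 8.1.3, 8.2 and 8.5 by amending the last three sentences of 8.1.3, including the one that refers disputes to the DSMB. Suggested text:

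> If the Investigator and the Sponsor's Medical Monitor disagree on seriousness or causality, both opinions are recorded. While the dispute is pending, the event is handled as serious and/or related for expedited reporting (Section 8.5) and expedited DSMB notice (Section 3.2) if either party so rates it. Neither party may downgrade the other's rating for this purpose. The case is referred to the DSMB for adjudication of the final classification; reporting does not wait for its response.

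For seriousness this applies the rule already in 8.2. For causality it is a new rule and should be presented as such. It governs reporting only, so adjudication still decides the final classification.

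The cost is a one-paragraph amendment with matching safety-plan wording, and a few more expedited reports. Because Protocol 6.4 allows staff who handle SUSAR reporting to be unblinded, those extra reports may unblind such staff for the cases concerned.
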